## PROTOCOL SUMMARY

Protocol Title (Short Title)	Remote sleep assessment in adults at risk for dementia using the ANNE Vital Sign System
Protocol Number	5366
Phase	Initial Phase
Study Design	Prospective cohort study
Study Duration	3 years
Setting	Home-based assessment of sleep apnea.
Sample Size	750
Main Inclusion Criteria	Enrolled participants in the Canadian Therapeutic Platform Trial for Multidomain Interventions to Prevent Dementia (CTU) and affiliated trials. All participants will be individuals ages 60-85 classified as Not Dementia according to Canadian Consortium for Neurodegeneration in Aging (CCNA) criteria and classified as being at increased risk of dementia.
Primary Outcome(s):	The primary objective of this study is to test the hypothesis that sleep apnea is associated with accelerated cognitive decline in older adults at risk for dementia
Secondary Outcome(s):	Sex-stratification will be used in analyses as appropriate. Qualitative feedback forms will be used to collect information about participant ease of use and experience with the ANNE Vital Sign System.
Investigational Product and Planned Use	
The Advanced NeoNatal Epidermal (ANNE) Vital Sign System is a wireless remote monitoring system intended for use by researchers and healthcare professionals for continuous collection of physiological data in home and professional healthcare settings. The ANNE Vital Sign System integrates simultaneous synchronized ambulatory measurement of electrocardiography, photoplethysmography with derived pulse oximetry, pulse arrival time with derived beat-to-beat blood pressure, triaxial accelerometry, respiratory rate, and temperature, which would enable accurate measurement of sleep apnea. The ANNE Vital Sign System is non-invasive, flexible, easy to use, comfortable, and skin safe.
 
All individuals enrolled in CTU and affiliated trials will be eligible to complete the ANNE Vital Sign System sleep assessment unless excluded by an additional set of exclusion criteria specific to the ANNE Vital Sign System.
 
Recruiting sites for CTU and affiliated trials will refer potential participants to Sunnybrook Research Institute (SRI) to obtain

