## 4 STUDY DESIGN

### 4.1 General Design

The Canadian Therapeutic Platform Trial for Multidomain Interventions to Prevent Dementia (CTU) is a Canada-wide study of older adults at risk for dementia, undertaken by the Canadian Consortium on Neurodegeneration that will begin recruitment in May 2022 and is anticipated to recruit 750 participants from May 2022-April 2024. The main goal of the CTU study is to serve as a shared platform to support studies of technologies and interventions to prevent dementia. These sub-studies are able to share CTU resources for recruitment and outcome ascertainment.

Participants in CTU and affiliated studies will be invited to participate in the ANNE Vital Sign System sub-study. CTU recruiting sites will refer potential participants to Sunnybrook Research Institute (SRI) to obtain informed consent and then prepare shipment of ANNE Vital Sign System and instructions to participant. The informed consent process will be conducted according to sections 7.1 and 13.3 of this protocol. After study equipment and materials are shipped to and received by the participant, study staff will instruct the participant on the proper application and use of the ANNE Vital Sign System over remote video-conference. Specifically, study staff will instruct the participant to affix the ANNE Vital Sign System chest sensor to the participant's chest using electrode paste, the ANNE chest adhesive, and Tegaderm or similar. Study staff may ask participants to shave a 3"x2" section of their chest, but participants will be informed this is optional. Next, study staff will instruct the participant to affix the ANNE Vital Sign System finger sensor to the participant's non-dominant index finger using the ANNE limb adhesive. Participants will wear the sensors for 24 hours before removing it themselves at home and shipping back to Sunnybrook Research Institute using a pre-paid, pre-addressed package. This procedure will be completed at the Baseline visit and repeated 12 months later.

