### 5.1 Inclusion Criteria

The only inclusion criteria for this study is that participants must have consented and enrolled into a CTU affiliated study. There are no additional inclusion criteria. Individuals from CTU affiliated studies will be asked to confirm their enrollment in a CTU affiliated study as part of the informed consent process for this study.

For reference, inclusion criteria of CTU affiliated studies from which we will recruit may include, but are not limited to, the following list:

1. Ages 60-85
2. Sufficient proficiency in English or French
3. Technical ability to participate in remote assessments
4. Meets criteria for **No Dementia** and one of the following (according to CCNA Criteria):
  - a. Cognitively Unimpaired
  - b. Cognitively Unimpaired plus Subjective Cognitive Impairment
  - c. Mild Cognitive Impairment (MCI)
5. **AND** Classified as being at **increased risk** of dementia based on **at least one of the following**:
  - a. First-degree family history of dementia
  - b. Self-Reported or documented current and/or history at midlife (45-60 years) of the following risk factors:
    - i. Hypertension
    - ii. Hypercholesterolemia
    - iii. Body Mass Index > 30 kg/m^2
    - iv. Physical Inactivity
    - v. Insomnia
    - vi. Vascular-metabolic risk

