## 7 STUDY SCHEDULE AND PROCEDURES

### 7.1 Screening

At the time of their enrollment in CTU and affiliated studies at participating recruitment sites, individuals will be invited to indicate interest in participating in the ANNE Vital Sign System assessment. This will be done by secure video conference. If interested, participant contact information (name, telephone number, email address) and study ID will be sent by encrypted email to study staff at SRI. Study staff at SRI will confirm that there are no exclusions from the ANNE Vital Sign System assessment based on exclusion criteria specific to the ANNE Vital Sign System. Eligible participants will be asked to complete a separate informed consent process specific to the ANNE Vital Sign System study. For participants enrolled at French-speaking sites, a study team member from that site may assist SRI with participant communications.

For the purposes of this study, the consent process will be completed remotely. A site team member will email a copy of the consent form to the participant and schedule a phone/video call with the participant where they will walk through the key elements of consent with the participant and allow time for questions. If a participant is unable to receive the consent form, they will be mailed a hard copy. After walking through the key elements of consent and the participant has been given time and opportunity to consider participation and ask questions, they will be asked their willingness to participate. If agreeable, study staff and witness will sign and date two copies of the consent form, to be included in the shipment of study device and materials. For those who indicate a desire to participate, study staff will collect mailing information (name, address). Study staff will explain the mailing procedures and tell the participant to expect a package in the mail with tracking information emailed to them. This package will include two hard copies of the consent form, already signed by study staff and witness.

A second scheduled phone/video call with the participant will be conducted after the participant has received the package. During this call, key elements of the consent form will be reviewed again and participants will have additional opportunity to ask questions. If agreeable, participants will then sign both copies of the consent form, retain one for their records, and return the other in the return package with the device after completion of their measurements.

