## **7.2 Baseline/Enrollment**

Participants who are confirmed eligible and enrolled in CTU, are not excluded based on exclusion criteria specific to the ANNE Vital Sign System, and have completed the informed consent process will be provided instruction for use via video-conference with a member of the study team.

Study device will be sent to the participant via pre-paid package and tracked by a member of the study team.

As soon as possible after the study device and materials are received by the participant, study staff will instruct the participant on the proper application and use of the ANNE Vital Sign System via remote video-conference. Specifically, study staff will instruct the participant to affix the ANNE Vital Sign System chest sensor to the participant's chest using electrode paste, ANNE chest adhesive and Tegaderm or similar. Study staff may ask participants to shave a 3"x2" section of their chest, but participants will be informed this is optional. Next, study staff will instruct the participant to affix the ANNE Vital Sign System finger sensor to the participant's non-dominant index finger using the ANNE limb adhesive. Participants will wear the sensors for 24 hours before removing it themselves at home. Within 24 hours of removing the device, participants will be asked to fill out the Feedback Survey of Device Experience (Appendix 1), noted as optional. Finally, participants will be asked to return the device and feedback form by shipping back to SRI using a pre-paid, pre-addressed package. A new device and feedback form will be shipped to participants for their 12 month visit.

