### **10.2 Sample Size Considerations**

We anticipate that ~30% of participants (i.e. 210 participants) will have sleep apnea. Based on this, we estimate 86% power to detect a ~0.5 point difference in 12-month change in MoCA between participants with and without sleep apnea. As it is possible that treatment of sleep apnea may be a potential source of noise regarding longitudinal cognitive outcomes, we will adjust for this statistically by collecting information on treatment and adjusting as a covariate.

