### **10.5 Final Analysis Plan**

Cardiopulmonary data – .shrd file type – from the ANNE Vital Sign System will be downloaded locally by Sunnybrook Research Institute (SRI) who will convert to .edf file type, and manually annotate to extract information on sleep apnea. SRI will then upload processed data to the Longitudinal Online Research and Imaging System120 (LORIS). All uploads and downloads will be by Secure File Transfer Protocol (SFTP). We will quantify the apnea hypopnea index (AHI), oxygen desaturation index (ODI), hypoxemia burden, and time with oxygen saturation below 90% (O2<90). In addition, we will quantify 24-hour resting heart rate, and average heart rate, which are important physiological consequences of sleep apnea. Participants will be considered to have sleep apnea if their AHI is greater than or equal to 15. We will relate the presence of sleep apnea to change in MoCA scores between baseline and 12 months using t-tests. We will then use mediation analyses to test if any observed associations are mediated by effects of sleep apnea on average and daytime resting heart rate. Sex-stratification will be used in analyses as appropriate.

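### The pooled t-test takes no account of parent trial or assigned arm, so differences between parent trials can bias the apnea contrast in 12-month MoCA change

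*Combined protocol and SAP*

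**What the plan says.** The Protocol Summary defines the source population as "Enrolled participants in the Canadian Therapeutic Platform Trial for Multidomain Interventions to Prevent Dementia (CTU) and affiliated trials". Section 4.1 describes the platform: "The main goal of the CTU study is to serve as a shared platform to support studies of technologies and interventions to prevent dementia". Eligibility for the parent studies is indicative only. Section 5.1 says that "inclusion criteria of CTU affiliated studies from which we will recruit may include, but are not limited to, the following list", and the list offers several alternative routes to increased risk, among them BMI above 30, hypertension and insomnia.

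Section 10.5 gives the primary analysis: "We will relate the presence of sleep apnea to change in MoCA scores between baseline and 12 months using t-tests". Section 4.2 has the same test. Mediation through heart rate follows, and sex stratification where appropriate. Section 10.2 names one disturbing influence, saying "it is possible that treatment of sleep apnea may be a potential source of noise regarding longitudinal cognitive outcomes", and promises that "we will adjust for this statistically by collecting information on treatment and adjusting as a covariate".

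On timing, section 7.1 places the invitation "At the time of their enrollment in CTU and affiliated studies at participating recruitment sites". A consent call, shipping and a second call follow. Section 7.2 then has the device applied "As soon as possible after the study device and materials are received by the participant". No window is given relative to arm assignment or to the start of any parent intervention.

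No section uses parent trial, arm or intervention exposure as a covariate, stratum, exclusion or sensitivity analysis.

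**The concern.** The outcome covers 12 months in which some participants may receive an intervention meant to protect cognition. Section 10.2 accepts that treatment during follow-up can disturb the cognitive outcome, but provides only for treatment of apnea.

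There are two routes to bias.

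- **Between trials.** Parent trials with different eligibility may differ in apnea prevalence and also in intervention effect or expected MoCA change. Randomisation within each trial does not balance this across trials.
- **Timing.** If the recording that defines apnea is made after an intervention has begun, and the intervention alters AHI, then arm influences both exposure and outcome. The 12-month recording follows any parent intervention. The baseline recording might too. Sections 4.2 and 10.5 do not say which recording defines presence of apnea.

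At stake is whether a positive or null result can be attributed to apnea. Without arm and dates in the data set, the analyst could not tell which situation applied.

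**Working it through.** **Inputs from the documents.** N = 750 (5.3); about 30% with apnea, a difference of about 0.5 point and 86% power (10.2). SD, alpha and sidedness are not stated. Section 10.2 gives 210 with apnea, but 30% of 750 is 225, and 210 is 30% of 700. That mismatch is a separate matter.

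**The plan's own figure.** The 86% cannot be reproduced directly without an SD, so I solved for the SD it implies, assuming a two-sided 5% test and the normal approximation.

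- SE = 0.5 / (1.960 + 1.080) = 0.164
- 225 v 525: SD = 0.164 / √(1/225 + 1/525) = 2.06
- 210 v 490: SD = 1.99

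I use SE 0.164 and SD 2.06 below.

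**Bias from pooling trials.** The documents give no parent-trial effects, splits or prevalences, so everything here is assumed: two parent trials of 375, with half of trial 1 on an intervention that shifts MoCA change by *e* and no effective intervention in trial 2.

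Bias = *e* × 0.5 × (share of the apnea group from trial 1 − share of the non-apnea group from trial 1)

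| Apnea prevalence, trial 1 / trial 2 | Share of apnea group from trial 1 | Share of non-apnea group from trial 1 | Bias, *e* = 0.5 | Bias, *e* = 1.0 |
|---|---|---|---|---|
| 30% / 30% | 112.5/225 = 0.500 | 262.5/525 = 0.500 | 0 | 0 |
| 35% / 25% | 131.25/225 = 0.583 | 243.75/525 = 0.464 | 0.03 | 0.06 |
| 40% / 20% | 150/225 = 0.667 | 225/525 = 0.429 | 0.06 | 0.12 |

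The range is 0 to 0.12 point, or 0% to 24% of 0.5. The term *e* × 0.5 is simply the difference in mean MoCA change between the trials, so a difference of 0.25 to 0.5 point from any other cause gives the same bias.

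**Consequence, two-sided 5% test, SE 0.164.**

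| Bias | Type I error if there is no true difference | Power if the bias masks a true 0.5 |
|---|---|---|
| 0 | 5.0% | 86% |
| 0.03 | 5.4% | 82% |
| 0.06 | 6.5% | 76% |
| 0.12 | 11.2% | 64% |

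The bias masks the apnea difference when the trial with more apnea has the better MoCA course, and exaggerates it in the reverse case.

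**When arm is independent of apnea.** Expected bias is zero. With 1:1 assignment and 210 v 490, the SD of chance imbalance in arm is √(0.25 × (1/210 + 1/490)) = 0.041, so 95% of imbalances lie within ±8.1 percentage points. For a 0.5-point intervention effect that is at most 0.04 point. Adjusting for arm then adds little precision: with residual SD 2.0 and a 0.5-point effect, power goes from 85.3% to 85.8%.

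**A different question: effect modification.** Suppose half of all participants receive an intervention that removes a fraction *f* of the apnea-related excess decline. The pooled contrast is 0.5 × (1 − 0.5*f*).

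- *f* = 0.25: contrast 0.44, power about 76%
- *f* = 0.5: contrast 0.38, power about 63%

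This is an average over what participants receive, not confounding. A common apnea effect adjusted for trial and arm still averages over arms and does not restore 0.5. A control-only analysis would target the 0.5. With half of each group, SE = 2.06 × √(1/112.5 + 1/262.5) = 0.232, and power = Φ(0.5/0.232 − 1.96), or about 58%.

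**The case against.** The strongest reply is that the exposure is inferred. No section describes parent arms, randomisation, blinding or the fraction treated, and this device cohort is itself a sub-study of the platform. That stands. A reader might infer that MoCA change necessarily mixes the effect of apnea with that of the parent interventions. The documents do not support so strong a reading, because with apnea recorded before randomised assignment in a single trial the expected confounding is zero.

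The larger illustrated biases also need several things together: a prevalence gap of 10 to 20 percentage points, an intervention effect confined to one trial, and an effect of 0.5 to 1.0 point, which is one to two times the apnea difference the study is powered for. At 0.03 point the harm is negligible. If measured case-mix such as BMI explains why trials differ in prevalence, adjusting for it would also reduce the bias.

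A reader might further infer that section 3.1 seeks the association in people untouched by parent interventions. It does not say so; an average over participants as they are is a legitimate target.

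Likewise, 10.2 calls apnea treatment a potential source of noise and does not claim that it is the only one. Nor do the documents show that baseline recordings follow the start of an intervention. The interval is unspecified.

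None of this closes the gap. Eligibility may differ between parent studies, the recruits are pooled, and the plan provides no means of showing that the harmless case applies.

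**Conclusion.** The concern holds as a gap in the analysis plan with possible, not certain, bias. Under the assumed values the bias is 0 to about 0.12 point, or 0% to 24% of the planned 0.5. At the upper end, type I error would be about 11%, or power about 64% if the effect is masked. These figures rest on two equal parent trials, assumed prevalences and intervention effects, and an SD of 2.06 back-solved from the stated power.

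The fall in the contrast to 0.44 or 0.38 should not be counted as bias: it is effect modification, and adjustment for trial and arm does not remove it. The change is worth making because it is cheap, and because dates not captured as the study runs may be hard to recover.

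**What to change.** **Sections 4.2 and 10.5.** Obtain parent trial and assigned arm from CTU, after unblinding if the parent trial is blinded. Replace the t-test with a regression of 12-month MoCA (or change) on baseline apnea status, baseline MoCA, and parent trial with arm within trial. This model can also carry the apnea-treatment covariate promised in 10.2, which a t-test cannot. Because apnea is not randomised, state that the contrast is conditional on baseline MoCA. Name the baseline recording as the one that defines exposure.

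**Sections 7.1 and 7.2.** Record the dates of MoCA, device recording and parent-intervention start, and flag baseline recordings made after that start.

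**Sensitivity analysis.** Prespecify an apnea-by-intervention or control-only analysis as supportive only. State that it addresses effect modification and has low power: about 58% for control-only if half of participants are controls and the SD is 2.06.

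**Cost.** Wording changes, a request to CTU for trial and arm, and the capture of dates. The adjusted analysis may have to wait for parent-trial unblinding, and a few degrees of freedom are used; how many depends on the number of trials and arms, which the documents do not give.

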## **4.2 Primary Outcomes/Endpoint(s)**

We will quantify the apnea hypopnea index (AHI), oxygen desaturation index (ODI), hypoxemia burden, and time with oxygen saturation below 90% ( $O_2 < 90$ ). A participant will be considered to have sleep apnea if their AHI is greater than or equal to 15. In addition, we will quantify 24-hour resting heart rate, and average heart rate, which are important physiological consequences of sleep apnea.

As part of their participation in CTU, participants will undergo a Montreal Cognitive Assessment (MoCA) at baseline and after 12 months. We will relate the presence of sleep apnea to change in MoCA scores between baseline and 12 months using t-tests. We will then use mediation analyses to test if any observed associations are mediated by effects of sleep apnea on average and daytime resting heart rate.

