	
informed consent and then prepare shipment of ANNE Vital Sign System and instructions to participant. After study device and associated materials are shipped to and received by the participant, study staff will instruct the participant on the proper application and use of the ANNE Vital Sign System over remote video-conference according to manufacturer recommendations. Participants will wear the sensors for 24 hours and this procedure will be completed at the Baseline visit and repeated at the Month 12 visit.

Statistical Analysis:
	
Cardiopulmonary data – .shrd file type – from the ANNE Vital Sign System will be downloaded locally by Sunnybrook Research Institute (SRI) who will convert to .edf file type, and manually annotate to extract information on sleep apnea. SRI will then upload de-identified, processed data to the Longitudinal Online Research and Imaging System120 (LORIS). All uploads and downloads will be by Secure File Transfer Protocol (SFTP). We will quantify the apnea hypopnea index (AHI), oxygen desaturation index (ODI), hypoxemia burden, and time with oxygen saturation below 90% (O2<90). Participants will be considered to have sleep apnea if their AHI is greater than or equal to 15. We will relate presence of sleep apnea to 1-year change in cognition measured using the Montreal Cognitive Assessment (MoCA), collected as part of CTU and affiliated trials. Sex-stratification will be used in analyses as appropriate.

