### **3 STUDY OBJECTIVES**

#### **3.1 Primary Objective**

The primary objective of this study is to test the hypothesis that sleep apnea is associated with accelerated cognitive decline in older adults at risk for dementia. We will measure sleep apnea at baseline and 12 months later and relate this to cognitive function at the same time points.

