Cardiopulmonary data – .shrd file type – from the ANNE Vital Sign System will be downloaded via Bluetooth locally to an iOS tablet, then converted to .edf file type, and manually annotated to extract information on sleep apnea. SRI will then upload de-identified processed data and summary measures to the Longitudinal Online Research and Imaging System^120 (LORIS) using the media uploaded functionality. All uploads and downloads will be by Secure File Transfer Protocol (SFTP).

LORIS is a web-based database solution for neuroimaging and other research data that is physically located at McGill University in Montreal. It will store data that has been processed to remove any direct identifiers of an individual study participant. Study subjects will be assigned a unique coded study identification number (LORIS Project Study Centre ID (PSCID)) that will be used to store their data. Local study sites will be responsible for storing all participant identifying information (name, contact, e-mail address) in secured encrypted databases and to maintain the master file that links the participant to their unique LORIS PSCID.

Study data may be sent to and received from investigators at other academic institutions for the research purposes explained in this protocol. Additionally, some study data may be shared with the device manufacturers to facilitate analyses in support of the academic aims above. Any study data about participants that is sent outside of the participating institution will have a code and will not contain name or address, or any information that directly identifies participants. All data transfer will be achieved through secured FTP, secure VPN or an encrypted hard drive.

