## **4.3 Secondary Outcomes/Endpoint(s)**

Sex stratification will be used in analyses as appropriate.

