## **7.3 Study visits/Follow up**

Baseline procedures will be repeated 12 months later. Participants at either time point with an AHI of  $\geq 15$  as determined by our quantification will be called via telephone by study staff to be a) notified that they have a high probability of having sleep apnea and if accompanied by severe sleepiness should refrain from driving, b) encouraged to contact their family physician for clinical evaluation where an official diagnosis of sleep apnea may or may not be made, and c) asked to notify study staff if they obtain treatment, unless treatment is obtained after their month 12 visit. Participants will be reminded that data collected as part of this study are for research purposes only and may not constitute a diagnosis of sleep apnea.

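### Does the plan need a prespecified severity analysis because it computes AHI, ODI, hypoxemia burden and time below 90% saturation but tests only AHI ≥15 against MoCA change?

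*Combined protocol and SAP*

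**What the plan says.** Section 4.2 opens with the measurements: "We will quantify the apnea hypopnea index (AHI), oxygen desaturation index (ODI), hypoxemia burden, and time with oxygen saturation below 90" per cent. It then defines the exposure: "A participant will be considered to have sleep apnea if their AHI is greater than or equal to 15". Section 10.5 repeats both and gives the test: "We will relate the presence of sleep apnea to change in MoCA scores between baseline and 12 months using t-tests". The Protocol Summary agrees: "We will relate presence of sleep apnea to 1-year change in cognition measured using the Montreal Cognitive Assessment". The mediation analysis that follows in 10.5 again takes sleep apnea as the exposure, with heart rate as the mediator; no oxygen measure enters it.

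The hypothesis in 10.1 compares participants with sleep apnea to those without. Section 10.2 gives 86% power for a difference of about 0.5 MoCA points between those same two groups. The objective in 3.1 is looser: "We will measure sleep apnea at baseline and 12 months later and relate this to cognitive function at the same time points". It names no severity measure and no model. Section 4.3, on secondary outcomes, has one line: "Sex stratification will be used in analyses as appropriate".

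The measures are kept. Under 4.1, "SRI will then upload de-identified processed data and summary measures" to the shared database, so they will be available for later work.

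**The concern.** Four measures stand under a heading for primary outcomes, yet they are exposures, and three of them are never used again. A reader cannot tell whether a later result on ODI or hypoxemia burden was planned. Four such tests at 0.05 with no plan carry a false-positive chance between 5% (fully dependent) and 1 − 0.95⁴ = 18.5% (independent).

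Cutting a continuous measure in two usually discards information. In an observational cohort, a graded relation between severity and decline would also support the hypothesis in a way that a two-group comparison cannot. The data will exist anyway, so a few regressions look like a cheap gain. What is at stake is supporting evidence and clarity of reporting; the primary result is not in question.

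**Working it through.** **Inputs.** From 10.2: about 30% exposed, given as 210; a difference of about 0.5 points; power 86%. Since 210/0.30 = 700, I use 210 against 490. Not in the documents, so assumed: two-sided 0.05, the SD of MoCA change, and a normal exposure (AHI after transformation) with the cut at its top 30%.

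**1. The plan's own figure.** The SD that gives 86% is 0.5 / [√(1/210 + 1/490) × (1.960 + 1.080)] = 0.5 / (0.0825 × 3.040) = 1.99. With 225 against 525 (30% of 750) it is 2.06. I take SD 2.0. The standard error is then 2.0 × 0.0825 = 0.165, the noncentrality is 0.5/0.165 = 3.03, and power is Φ(3.03 − 1.96) = 85.8%. The stated 86% is attainable. At 210 against 490, power runs from 98% at SD 1.5 to 52% at SD 3.0.

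**2. Information kept by the split.** The cut is at z = 0.524, where the normal density is 0.3477. If the effect is linear, the split keeps 0.3477² / (0.3 × 0.7) = 0.576 of the information.

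**3. Continuous model, linear effect.** The groups differ by 0.3477/0.3 + 0.3477/0.7 = 1.656 exposure SDs, so a 0.5-point gap means a slope of 0.5/1.656 = 0.302 per SD and a correlation of 0.302/2.0 = 0.151. Noncentrality is √700 × 0.151/√(1 − 0.151²) = 4.04, and power is Φ(4.04 − 1.96) = 98.1%.

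**4. Continuous model, step at 15.** Noncentrality falls to 3.03 × √0.576 = 2.30, and power to Φ(2.30 − 1.96) = 63%.

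**5. Side by side.** The true group gap is 0.5 points in every row. The range adds simulations with log-normal AHI (log-SD 1.0 to 1.25) analysed as log(AHI+1).

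| Shape of effect | Continuous, normal exposure | Range | Split |
|---|---|---|---|
| Linear | 98% | 96–98% | 86% |
| Rising only above 15 | 88% (simulated) | 88–92% | 86% |
| Step at 15 | 63% | 63–68% | 86% |

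**6. Would a significant slope show that decline grows with severity?** No. Under a pure step, decline does not deepen beyond the cut, yet the slope is significant 63–68% of the time. To separate the two, one needs a slope among the 210 at or above 15. A standard normal cut below at 0.524 has mean 1.159 and variance 1 + 0.524 × 1.159 − 1.159² = 0.265, so SD 0.514. With the linear slope and residual SD 1.98, noncentrality is 0.302 × 0.514 × √210 / 1.98 = 1.14, which gives about 21% power.

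**7. Measurement error.** Assuming a poorly measured AHI makes the continuous model look better relative to the split. In a bivariate normal model with 30% above the cut, reliability 0.8 implies sensitivity 79% and specificity 91%; 0.6 implies 69% and 87%. Section 2.3 reports 90% and 98% at AHI 15, which points to roughly 0.95 (90% and 96%) to 0.99 (95% and 98%). At 0.98 (10,000 simulations, N = 700), continuous against split is 98 against 85% for a linear effect, 88 against 86% for one rising only above 15, and 62 against 78% for a step.

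**The case for a change.** The best case for a change does not depend on power. The protocol itself puts these measures first under primary endpoints, so it should say what they are for, even if the answer is only descriptive. Summary data go to a shared database, others may gain access after an embargo (section 14), and the consent form covers future analyses (7.1, 13.3). Unplanned testing is therefore a realistic prospect, and a line of text costs almost nothing.

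Much of this stands. The measures have no stated role, and their heading is loose. But the 18.5% attaches to analyses the plan does not contain, and the ordinary safeguard is to report them as exploratory, which needs no amendment. Section 14 also asks for protected planned projects to be listed and limits access to the project requested. That is not statistical prespecification, but it narrows the room for selective testing.

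Night-to-night variation could lower the reliability of a single recording below what 2.3 suggests, and that would favour the continuous model. The documents give no figure for it; 2.3 mentions repeatability testing without results.

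An added regression would also bring its own difficulties. Participants at or above 15 are telephoned, encouraged to seek evaluation, and "asked to notify study staff if they obtain treatment, unless treatment is obtained after their month 12 visit". Care during follow-up may therefore change with the exposure itself, and a slope across the whole AHI range would need careful reading with or without the treatment covariate planned in 10.2.

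**Conclusion.** The concern describes the text correctly but does not call for a change. The primary exposure, hypothesis, power and test agree with one another. AHI ≥15 is also the threshold for which 2.3 reports diagnostic accuracy. Adding severity models would leave the primary test and its power as they are.

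The gain in power is about 12 points (98% against 86%) if the effect is linear, small (about 2 to 6 points) if it starts only above 15, and a loss of 18 to 23 points if it is a step. In none of these cases would a significant slope by itself show that decline deepens with severity. For ODI, hypoxemia burden and time below 90% saturation, the documents allow no calculation of gain.

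These sizes rest on an SD of about 2.0 back-solved from the stated power, 210 against 490 participants, two-sided 0.05, and assumed AHI distributions and effect shapes. The conclusion itself rests mainly on the match between hypothesis and test, which needs none of those assumptions. The missing labels are a gap that analysts can fill sensibly by presenting the other measures as descriptive or exploratory.
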